4 STUDY DESIGN

4.1 Overall Design

This is a double-blind, randomized, placebo-controlled, multiple site, sequential panel, single and multiple dose trial of MK-2060 in older adult participants (age ≥ 40 and ≤ 80 for Part 1 and ≥ 18 and ≤ 80 for Part 2; men and women of non-child bearing potential) with ESRD on HD to be conducted in conformance with Good Clinical Practice. The study will evaluate the safety and tolerability, pharmacokinetics (PK), and pharmacodynamics (PD) of single and multiple dose IV administration of MK-2060 in older adult participants with ESRD.

Part 1: Part 1 of the trial will consist of up to 3 panels. In all panels, 8 participants will be randomized to receive a single dose of MK-2060 or placebo (0.9% sodium chloride infusion, USP sterile saline) in a treatment ratio of 3:1 (6 active and 2 placebo). Each participant may only participate in one panel of the study.

Participants in all panels will be domiciled for ~52 hours after study drug administration for safety/tolerability monitoring. Participants in all groups/panels will be closely monitored for safety and tolerability, including safety labs, local lab aPTT and PT results, physical exam to check incidence of bleeding, vital signs (VS) and 12-lead ECG, as well as local infusion site reactions and for systemic reactions to infusion.

There will be approximately a 28-day period (+/- 2 days) [including 21 days (+/- 2 days)] safety data review and approximately 7 days for dosing escalation decision) between dosing the last cohort in a panel and dose administration in the next panel to evaluate safety, tolerability, and available PK data. The decision to proceed to the next panel will be based upon acceptable safety and tolerability data collected over at least a 21-day (+/- 2 days) observation period for at least 7 participants in the previous panel, including local lab aPTT, PT, and hemoccult test review. Plasma pharmacokinetic data will be reviewed on an ongoing basis and at least 14 days of PK data from at least 7 participants in Panel A (8 mg dose) will be evaluated prior to proceeding to the next panels. Panel C (40 mg dose) will not be dosed until at least 21 days of safety, tolerability, PK, and PD data from the 40mg IV panel in the ongoing PN001 (Panel I) has been reviewed.

Part 2: Part 2 will be the first study of multiple dosing of MK-2060 in older adult patients with ESRD on HD. In this part, approximately 20 participants will be randomized to a 3 times per week for the 1st week and then once weekly dose for 3 weeks of MK-2060 or placebo (0.9% sodium chloride infusion, USP sterile saline) in a treatment ratio of 3:1 (15 active and 5 placebo) for total of 4 weeks of dosing. Participants will receive a loading dose up to 25 mg IV MK-2060 or placebo for a total of 3 doses in week 1 and a weekly maintenance dose up to 25 mg IV MK-2060 or placebo in weeks 2-4. Participants will not be dosed until 14 days of safety data and available PK data from at least 6 participants in the 40mg IV panel (Part 1 Panel C) of this trial has been reviewed. Participants who have completed Part 1 Panel A, B, or C may be enrolled in Part 2 of the study with joint agreement of the Investigator and the Sponsor.

Participants will be domiciled for the 1st week until ~ 24 hours post the third dose and for ~24 hours after each study drug administration in weeks 2-4 for safety/tolerability monitoring. Participants may be domiciled longer pending the investigator requirements and/or the preference of the participant. Participants will be closely monitored for safety and tolerability, including safety labs, local lab aPTT and PT results, physical exam to check incidence of bleeding, vital signs (VS) and 12-lead ECG, as well as local infusion site reactions and for systemic reactions to infusion. All participants in this study will be followed through approximately 3 months after the last study dose (Dose #6) for safety and tolerability, including all adverse experiences, safety labs, local lab aPTT and PT results, physical exam to check incidence of bleeding, vital signs (VS) and 12-lead ECG.

The trial design is depicted in [Figure 1, Figure 2 and Table 1]. For all panels in Part 1 and Part 2, participants will be followed for approximately 164 days or 90 days post the last dose of study drug respectively. Blood samples will be collected for MK-2060 plasma PK and PD to assess aPTT/PT levels, fibrin generation, and FXI activity levels.

The precise timing of safety and tolerability measurements, PK and PD samples may be altered during the course of the study based on newly available data (i.e., to obtain data closer to the time of peak concentrations or to better describe the half-life of the compound).

Because this is a Phase 1 assessment of MK-2060 in humans, the pharmacokinetic (PK), pharmacodynamic, and safety profiles of the compound are still being elucidated. This protocol is therefore written with flexibility to accommodate the inherent dynamic nature of Phase 1 clinical studies. Refer to Section 8.11.7 for examples of modifications permitted within the protocol parameters.

Specific procedures to be performed during the study, as well as their prescribed times and associated visit windows, are outlined in the SoA in Section 1.3. Details of each procedure are provided in Section 8.

4.2 Scientific Rationale for Study Design

The main objectives of this study are to evaluate safety, tolerability, PK, and PD of MK-2060 after IV administration of single and multiple doses in older adult (ages ≥ 40 and ≤ 80 for Part 1 and ≥ 18 and ≤ 80 for Part 2) men and women of non-child bearing potential (WONCBP) with ESRD on HD. PD effects on aPTT, PT, FXI activity, and fibrin generation will be explored. Up to approximately 44 older adult participants with ESRD on HD who meet study eligibility criteria may be enrolled in this study.

MK-2060 is being developed for the prevention of thrombotic complications in ESRD patients, thus the primary aim of this study is to evaluate safety, tolerability, PK, and PD of MK-2060 in this patient population.

We do not anticipate renal impairment, HD, or age to significantly alter the PK and PD of MK-2060. As discussed above, PN001 has demonstrated MK-2060 to be generally safe and well-tolerated in normal healthy subjects. Based on preliminary analysis, MK-2060 achieved mean maximum concentration at 1hr (end of infusion) after IV infusion, followed by a bi-phasic terminal phase with apparent mean half-life of ~29 to 39 days. MK-2060 clearance was ~0.23 L/day, consistent with reported CL of mAb. As renal elimination is typically an insignificant pathway for IgG mAbs due to their large size, the clearance of MK-2060 is not expected to change in renal impaired subjects or subjects on hemodialysis. Furthermore, assessment of the clotting cascade in subjects with ESRD has demonstrated that FXI levels are not significantly altered [Vaziri, N. D., et al 1994]. In PN001, MK-2060 volume of distribution was estimated as 11 L, slightly larger than the reported volume of distribution for mAb. [Dirks, N. L. 2010]. It could be possible that kidney failure or HD might impact volume of distribution, due to fluid retention, although we do not anticipate this to have a major effect. As MK-2060 is a monoclonal antibody age is also unlikely to alter PK and PD. The impact of renal impairment, HD, and age on MK-2060 PK and PD will be further

assessed by comparing data in this study to the data in young normal healthy subjects in PN001. IONIS has demonstrated using an FXI anti-sense oligo (ASO) that inhibition of the FXI pathway in ESRD patients on HD (mean age of 61 years) is generally safe and well-tolerated [Bethune, C., et al 2017]. Thus, the study of MK-2060 in older adult patients with ESRD on HD is well supported.

The rationale to limit recruitment to males and WONCBP is that developmental and reproductive toxicology studies in animals have not been completed.

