
Part 1:
 
• Objective: To compare the plasma pharmacokinetics of MK-2060 following a single dose IV administration in older adult participants with ESRD on HD to participants with normal renal function (historical controls in PN001).• Estimation: In older adult participants with ESRD on HD, PK parameters (e.g. AUC_{0-∞}, Cmax) of MK-2060 following administration of a single dose will be estimated and compared to participants with normal renal function (historical controls in PN001).	
• Part 1: MK-2060 plasma AUC_{0-∞}, AUC₀₋₁₆₈, Cmax, C₁₆₈, T_{max}, terminal t_{1/2}, CL and V_z

Objectives	Endpoints
Tertiary/Exploratory	

Objective: Part 1: To explore the effect of MK-2060 given as a single IV dose on Factor XI (FXI) activity levels. Part 2: To explore the effect of MK-2060 given as multiple IV doses on Factor XI (FXI) activity levels.	a. FXI activity level fold change from baseline

Objective: Part 1: To explore the effect of MK-2060 given as a single IV dose on fibrin generation. Part 2: To explore the effect of MK-2060 given as multiple IV doses on fibrin generation.	b. Fibrin Generation Assay (FGA)

Objective: Part 1: To explore the effect of MK-2060 given as a single IV dose on prothrombin time (PT). Part 2: To explore the effect of MK-2060 given as multiple IV doses on prothrombin time (PT).	c. PT fold change from baseline

Objective: Part 1: To explore the effect of MK-2060 given as a single IV dose on biomarker(s) of inflammation (e.g., hsCRP). Part 2: To explore the effect of MK-2060 given as multiple IV doses on biomarker(s) of inflammation (e.g., hsCRP).	d. hsCRP reduction from baseline

Objectives	Endpoints

Objective: Part 1: To explore the effect of MK-2060 given as a single IV dose on time to hemostasis after decannulation of the hemodialysis vascular access site in ESRD patients. Part 2: To explore the effect of MK-2060 given as multiple IV doses on time to hemostasis after decannulation of the hemodialysis vascular access site in ESRD patients.	e. Time to adequate hemostasis after decannulation of vascular access compared to baseline

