In Part 2 (multiple dose), in order to mimic the therapeutic setting, 3 doses given on Days 1, 3, and 5 will be studied in addition to the weekly maintenance dose. A weekly maintenance dosing frequency was selected to reduce the peak to trough ratio without posing a significant burden to ESRD patients who undergo dialysis 3 times a week and can receive an IV infusion concurrent with dialysis. A less frequent dosing interval would result in higher peak concentrations and patients being sustained at maximal FXI inhibition levels longer, which could potentially increase bleeding risk in this vulnerable population. For anticoagulants, it is desirable to achieve near target anticoagulation as soon as therapy is initiated. Given the half-life of ~18 days observed in Part 1 of PN004 and the dosing frequency of QW, without the 3 doses given during week 1 (loading dose) it would take weeks to achieve steady state exposure and target anticoagulation. Thus, the 3 doses during week 1 are introduced to help achieve desired anticoagulation immediately after initiation of therapy.

Participants will be discharged following the ~52- or ~24-hour (24 hours after last dose for Week 1 and 24 hours after each dose in Weeks 2-4) in-clinic period after dosing for Part 1 or Part 2 accordingly, but they will continue to be monitored throughout the trial period and return to the site post-dose as specified in the SoA (safety evaluations as indicated in the flow chart (including repeat physical examinations, infusion reaction assessments, laboratory safety assessments, hemoccult, local lab aPTT and PT tests).

Following discharge, the following measures are being taken in this protocol to ensure the safety of study participants:

- Participants will be informed that they could be taking an anticoagulant as a participant in this trial, and that this might increase the risk of bleeding as might occur in surgery, dental procedures, or strenuous exercise/contact sport activities.
- Participants will be excluded if they have planned significant dental procedures, including surgery, or other planned surgical procedures within duration of participation in the trial.

- Participants will be required to avoid scheduling any surgical or dental procedures, and to avoid strenuous physical activity and contact sport activities for the duration of the trial.

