6.6.1 Stopping Rules

If any of the following events occur, dose escalation in Part 1 or subsequent dosing in Part 2 will be stopped to review additional safety data:

- If one or more treatment related infusion adverse events of severe intensity occurs.
- If one or more treatment related SAEs occurs, dose escalation will be stopped and a meeting to review available safety data by the investigator and Sponsor will be required.
- Two (2) or more participants within a Panel in Part 1 (at the same dose level) or Part 2 report Severe Non-Serious Adverse Events considered related to the study drug by the investigator.
- An increase in local lab aPTT > 4.0 -fold versus screening baseline as confirmed after repeat measurement in 2 or more subjects in a panel in Part 1 or in Part 2. Local lab aPTT measured at Screening Visit 1 should be used as baseline value.
- An increase in local lab PT > 1.5 -fold versus screening baseline as confirmed after repeat measurement in 2 or more subjects in a panel in Part 1 or in Part 2. Local lab PT measured at Screening Visit 1 should be used as baseline value.

In severe FXI-deficient populations, aPTT prolongations greater than 3-fold have been observed (050RJ8). Using the same PD aPTT assay utilized in PN001 and to be used by the central lab in this study, samples of pooled normal human plasma were compared to those from FXI-deficient patients, which were tested individually [Ellsworth K 2018]. In normal human plasma, the clot time ranged between 31.8 and 36.4 seconds. In plasma from FXI deficient patients, the clot time ranged between 99.5 and 128.1 seconds, which corresponded to a range of 2.9 to 3.9-fold prolongation in aPTT compared to that of the normal human plasma. From data collected in PN001, it appears that higher doses of MK-2060 provide similar inhibition as the severe FXI-deficient phenotype, evidenced by MK-2060-associated increases in aPTT (local lab) up to 3.9-fold at the highest doses in PN001. These aPTT prolongations occurred in the absence of prolongation of PT and were associated with $>95\%$ inhibition of FXI activity, with no evidence of MK-2060-related AE. Therefore, the stopping criteria based upon an aPTT is >4 -fold after repeat measurement in 2 or more subjects in a panel.

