9.6 Statistical Methods

Safety

Summary statistics and plots will be generated for raw laboratory safety tests, ECGs, and/or VS as well as for change from baseline, as deemed clinically appropriate. Depending on the safety parameter, the difference from baseline will either be computed on the original scale (raw change from baseline) or on the log scale and back-transformed for reporting (percent change from baseline).

Pharmacokinetics

Model-Based PK Summary

Part 1:

SD PK of participants with ESRD from the present study will be compared with historical SD PK data (P001) in healthy participants.

Separately for each PK parameter, individual values of AUC_{0-∞}, AUC_{0-168hr}, C_{max}, and C_{168hr} will be natural log-transformed and evaluated with a linear fixed effects model containing a categorical effect for population (ESRD on HD, healthy) and dose (8mg IV, 20mg IV and 40mg IV) and dose by population interaction. The fixed effects model will also contain a categorical effect for sex and a continuous effect for age. The present study will enroll older male and female subjects, while P001 enrolled younger male subjects. Sex and age are not expected to impact PK. An unstructured covariance matrix will be used to allow

for unequal population variances via the REPEATED and GROUP statement in SAS PROC MIXED. Kenward and Roger's method will be used to calculate the denominator degrees of freedom for the fixed population effect (DDFM=KR). Ninety-five percent (95%) CIs for the least squares means for each population by dose will be constructed on the natural log scale and will reference the t-distribution. Exponentiating the least-squares means, and their corresponding 95% CIs will yield estimates for the population geometric means and confidence intervals about the geometric means on the original scale.

Part 2:

Geometric means and 95% confidence intervals (based on a t-distribution) will be provided for AUC0-168, Cmax, and C168 obtained following the last multiple dose. Median, minimum, and maximum will be provided for Tmax.

Secondary Analysis: Comparison to Healthy Subjects

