To compare subjects with ESRD on HD to subjects with normal renal function at the same dose level, a two-sided 90% confidence interval for the true difference in means (ESRD on HD – normal renal function, at the same dose level) will be calculated for each PK parameter using the mean square error from the PK model described above and referencing a t-distribution. For each dose level of ESRD on HD, these confidence limits will be exponentiated to obtain the 90% confidence interval for the true ratio of geometric means (ESRD on HD/normal renal function, at the same dose level) for each PK parameter.

Dose Proportionality

An exploratory analysis will be conducted to preliminarily assess dose proportionality of MK-2060 AUC0- ∞ , AUC0-168hr, Cmax and C168hr in ESRD on HD participants, using the power law model. Separately for each PK parameter, individual PK values will be natural log transformed and evaluated with a linear regression model having ln(dose) as an explanatory variable. A least square estimate and 95% confidence interval for the slope associated with ln(dose) will be obtained from the model.

A plot of the observed PK data versus dose will be provided along with an estimated regression line on the raw scale and a 95% Schéffe confidence band.

Descriptive Statistics

Individual values will be listed for each PK parameter (including Tmax and apparent terminal t_{1/2}, CL, Vz) by treatment, and the following (non-model-based) descriptive statistics will be provided: N (number of subjects with non-missing data), arithmetic mean, standard deviation, arithmetic percent CV (calculated as 100 x standard deviation/arithmetic mean), median, minimum, maximum, geometric mean, and geometric percent CV (calculated as 100 x sqrt(exp(s²) - 1), where s² is the observed variance on the natural log-scale).

Pharmacodynamics

Secondary Hypothesis

Part 1:

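### Half-life and volume are listed for the ESRD-versus-PN001 comparison, but the SAP gives neither a cross-study ratio nor a confidence interval

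*Combined protocol and SAP*

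**What the plan says.** Section 3 sets a Part 1 secondary objective of comparing single-dose PK in ESRD participants with PN001 historical controls. Its endpoint list is AUC0-∞, AUC0-168, Cmax, C168, Tmax, "terminal t_{1/2}, CL and V_z".

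Section 9.6 (and 9.1 in the same terms) fits the population-by-dose model to four of these: "individual values of AUC_{0-∞}, AUC_{0-168hr}, C_{max}, and C_{168hr} will be natural log-transformed". The 90% CI for the ESRD/healthy ratio is promised for each PK parameter, but it is computed "using the mean square error from the PK model described above and referencing a t-distribution", so it exists only for those four. Individual Tmax, t1/2, CL and Vz values are listed, with non-model-based descriptive statistics by treatment.

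On what might differ, Section 4.2 says of volume: "It could be possible that kidney failure or HD might impact volume of distribution, due to fluid retention". It adds that no major effect is anticipated. The same section gives PN001 an "apparent mean half-life of ~29 to 39 days". Section 4.3.5, justifying the loading doses, writes: "Given the half-life of ~18 days observed in Part 1 of PN004". The documents do not comment on the difference.

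**The concern.** A parameter listed for a between-study comparison should have a stated between-study estimate. For half-life and Vz there is none, and half-life is the parameter for which the protocol itself reports clearly different values in the two populations.

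Followed as written, the clinical study report would show half-life and Vz summaries for ESRD participants, and any comparison with PN001 would be made by eye. Section 2.1 says the data will aid dose selection in later trials, and Section 4.3.5 already argues from half-life, so a ratio with its uncertainty would be useful to have.

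**Working it through.** **1. Endpoints against methods (Part 1).**

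| Parameter | Section 3 comparison | 9.6 model and 90% CI | 9.6 descriptive |
|---|---|---|---|
| AUC0-∞, AUC0-168, Cmax, C168 | listed | yes | yes |
| CL | listed | indirectly (CL = dose/AUC0-∞) | yes |
| t1/2, Vz | listed | no | yes |
| Tmax | listed | no | yes |

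**2. Size of the reported half-life difference.** 18/39 = 0.46 and 18/29 = 0.62, so half-life is 38% to 54% shorter in ESRD.

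**3. Does AUC0-∞ alone carry it?** Take t1/2 = ln2 × V/CL with the Section 4.2 values of 11 L and 0.23 L/day. This gives 0.693 × 11/0.23 = 33.2 days, inside 29 to 39. Two ways to reach 18 days:
- Through clearance: CL = 0.693 × 11/18 = 0.42 L/day, so the AUC0-∞ ratio is 0.23/0.42 = 0.54.
- Through volume: V = 0.23 × 18/0.693 = 6.0 L, so the AUC0-∞ ratio is 1.00.

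AUC0-∞ alone therefore does not identify a half-life change.

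**4. Do the four planned parameters together carry it?** This is an illustration, not a claim about the true cause. A two-compartment model with V1 3.33 L, V2 6.86 L, Q 1.23 L/day and CL 0.23 L/day matches the Section 4.3.3 figures for 40 mg. It gives Cmax 80 nM, C168 20 nM and AUC0-168 5,792 nM·hr (stated: about 80, about 20 and 5,800), with t1/2 33 days. Ratios to that base when t1/2 falls to about 18 days:

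| Route | Cmax | C168 | AUC0-168 | AUC0-∞ | Vz |
|---|---|---|---|---|---|
| CL doubled to 0.46 L/day | 1.00 | 0.74 | 0.87 | 0.50 | 1.09 |
| V2 cut to 2.44 L | 1.00 | 1.65 | 1.27 | 1.00 | 0.54 |

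The routes separate on three planned parameters: AUC0-∞, and C168 and AUC0-168, which move in opposite directions. If the ×/÷1.39 of Section 9.9 applied, an AUC0-∞ ratio of 0.50 would give 0.36 to 0.70 and a C168 ratio of 1.65 would give 1.19 to 2.29. Both exclude 1.

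**5. Which route do the documents suggest?** Section 4.3.3 equates 7920 µg/mL·day with 1.28 × 10⁶ nM·hr, which implies 148.5 kDa, so 25 mg is 168 nmol. Section 4.3.4 projects AUC0-168 of 8868 nM·hr after the last weekly dose in ESRD. CL = 168/8868 × 24 = 0.46 L/day. If that AUC is 90% of steady state (an assumption), CL = 0.41 L/day. Both are about 1.8 to 2.0 times the PN001 value, which points to clearance, and the planned AUC0-∞ ratio would reflect it.

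**6. Precision.** Section 9.9 first: half-width = t(0.95, 10 df) × √[(s² + (2s)²)/6]. With s = 0.199 this is 1.812 × 0.1817 = 0.329, or ×/÷1.39; with s = 0.169 it is 0.280 (stated 0.279), or ×/÷1.32. The plan's figures reproduce.

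For half-life the documents give no SD. Using the same formula over an assumed healthy log SD:

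| Assumed SD | Factor | 90% CI at 0.62 | 90% CI at 0.46 |
|---|---|---|---|
| 0.15 | 1.28 | 0.48 to 0.80 | 0.36 to 0.59 |
| 0.20 | 1.39 | 0.45 to 0.86 | 0.33 to 0.64 |
| 0.30 | 1.64 | 0.38 to 1.02 | 0.28 to 0.76 |

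These are per dose, 6 against 6, before the model's age and sex terms. PN001 enrolled younger men only, so adjusted intervals would probably be wider.

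**The case against.** The strongest reply is that the comparison is already adequate. The apparent driver, clearance, gets a ratio and a CI through AUC0-∞. The Section 3 estimation statement names AUC0-∞ and Cmax only as examples of what will be compared. Half-life and Vz are summarised. The Part 2 regimen came from PK/PD modelling (Section 4.3.4), and no passage shows a half-life ratio CI being used to set a regimen.

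Most of that stands, and it rules out several stronger readings that a reader might infer:
- *That the plan could not tell clearance from volume.* Steps 4 and 5 show that the planned ratios would give indirect evidence.
- *That the half-life difference gets no estimate at all.* Within-study estimates are planned; only the ESRD/PN001 ratio and its interval are absent.
- *That Section 4.2 foresaw a change in half-life.* It speaks only of volume and expects no major effect. Its mechanism, fluid retention, would raise volume and lengthen half-life, the opposite of what is reported.
- *That a PD objective lacks its analysis.* Section 4.2 says in one rationale sentence that the impact on PK and PD will be assessed against PN001, and Section 9 has no PD method for this. But the Section 3 objective against PN001 is limited to plasma PK, so this is a wording mismatch.

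The reply does not remove the mismatch between the Section 3 endpoint list and the Section 9 model.

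**Conclusion.** The point holds as an alignment gap between endpoint and method, and it is cheap to close. Half-life and Vz are listed endpoints of a secondary comparison but have no ESRD/PN001 ratio or CI, while the reported half-lives stand in a ratio of 0.46 to 0.62. The loss is a direct estimate with its uncertainty, not the ability to form a view on the cause.

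Whether the added interval would be decisive depends on an SD the documents do not give. At an assumed healthy log SD of 0.20 (doubled for ESRD), a ratio of 0.62 excludes 1; at 0.30 it does not. A ratio of 0.46 excludes 1 throughout the range shown. The planned sample size and the Section 9.9 precision figures are not in question.

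**What to change.** In Sections 9.1 and 9.6 (Part 1), add ln(t1/2) and ln(Vz) to the parameters fitted with the population-by-dose model, and name them in the 90% CI for the ESRD/healthy ratio. State that the CL ratio is reported as the reciprocal of the AUC0-∞ ratio.

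The cost is SAP wording and a few more runs of a model already planned. No participants, samples or procedures change: Table 7 already schedules Part 1 PK sampling to Day 150, and Section 2.2.2 says the clinical conduct of PN001 is complete, with preliminary PK and PD results available. The downside is that per-dose intervals may be wide, which the report should say.

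Optional and secondary: align Section 4.2 with Section 9 on PD. One way is to add a comparison with PN001 of central-lab aPTT fold change at 168 hours, by dose; Section 6.6.1 supports its feasibility ("Using the same PD aPTT assay utilized in PN001 and to be used by the central lab in this study"). The other is to remove the reference to PD from the Section 4.2 sentence.
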